# Study Design:

It will be a prospective, randomized, single-blinded study. The study device will be used for only 2 days during the post-surgery hospital stay. The patients will be followed until their 6 weeks post-op office visit. We aim to finalize the study in 6 months.

Before enrollment into the study: During their pre-operative visit, patients will fill out a short questionnaire (The Pain Catastrophizing Scale, PCS short form) to assess their eligibility for the treatment and create a homogenized group of patients. Inclusion criteria is detailed below. 50 patients who are eligible for the study will be enrolled by written consent. Informed written consent will be obtained by PI ([name]) and the health care professional team ([name] and [name],PA ) during pre-operation office visit.

Once the patient volunteers to enroll to the study, we will establish their patient-specific intensity during their pre-op office visit. We will plan to have patient establish their correct and comfortable intensity before their surgery. The device comes in a carrying case with all the set supplies. At the time of placement, a health care provider will place the pre-packaged sterile electrode roughly 7-10 cm above and below the knee for testing or just above and below the

dressing during on the operated knee. Each set of electrodes will then be connected via a lead wire to the stimulation device.

Establishing the correct and comfortable intensity before operation will be as follows: The stimulation device which has a large power button will be turned on but provide no initial signal intensity. The patient will then be instructed to use the "plus" arrow on the device to slowly increase the signal intensity. The goal is to reach a point of intensity that feels strong but comfortable. The best method is to continue to increase to the point where it becomes slightly uncomfortable and the patient may experience some muscle fasciculations. Once that point is reached, decrease the intensity slightly and then use that intensity for their treatment. This patient specific intensity will be recorded and used for the IFC treatment.

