Enrolled patients will be randomly assigned to either **i. IFC treatment or ii. Placebo group** after their surgery. Patients in both groups will continue their regular standard post-operative care in addition to the IFC (or placebo) treatment. In addition to their post-operative standard of care, both groups will receive IFC treatment (or Placebo treatment) two times a day, for two days during their post-op hospital stay.

i. For the IFC treatment group: In addition to their post-operative standard of care, the IFC group will receive IFC treatment two times a day, for two days during their post-op hospital stay. The specific intensity of the IFC signal is patient specific. We will use previously established intensity values for each patient.

Once the intensity is set the program will lock automatically after 1 minute of inactivity or can be manually locked using the "star" button on the device. There is some degree of subjectivity in this portion but that is what provides the user with a patient specific signal. The signal intensity can go up to "100" on the device. The device works for 30 minutes at a time. On the device there is a timer which shows the time and it will automatically turn itself off after 30 minutes. During the time when the device is working, the patient can do any regular activity such as ambulating, physical therapy or sleep without concern.

The electrode has an adhesive pad that can remain on the patient post-operatively if desired or can be removed and replaced for each treatment session. The individual electrodes are re-usable and will be assigned to each patient.

For Placebo group: The standard of care and their physical therapy will not be altered for the placebo group. One set of the devices are programmed to be the placebo devices. The placebo devices can give a sensory stimulus so that the patient will feel the device is being on, but they will not have the therapeutic stimulus. We will monitor and record the same post-surgery outcomes as for the treatment group.

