The outcomes will be monitored in the immediate post-operative period by the Orthopaedic Surgery clinical team at Wakefield Hospital as well as at during the first post-op visit by [name] office by physician assistant ([name],PA) and nurse practitioner ([name]). The average hospital stay for TKA patients in the hospital (Wakefield) varies between 48-72 hours post-operatively. Typically, patients have a follow-up visit at 2 weeks and 6 weeks after surgery in the Hutchinson Campus, Tower 1 Orthopaedic Surgery Department clinic.

1. Primary outcome will be the post-operative pain medication usage during the first 24 and 48 hours. Daily opioid use will also be accounted based on electronic medical record reported by the patient's nurse after providing the patient with the specific medication. In addition, patients will be asked to rate their pain based on a set VAS pain scale twice a day before the IFC treatment.

2. Secondary outcomes Fitness for discharge on postoperative day 1and day 2 this will be measured utilizing the AM-PAC "6-Clicks" Basic Mobility Inpatient Short Form. The "6-Clicks" tool measures functional ability by having an assessor rate a patient's ability to perform physical tasks such as turning over in bed, moving from a bed to chair, and climbing steps. Scores are tallied to a total of 24 possible points, giving a quantitative measure of a patient's ability to perform these tasks. We will also use the `time` to reach the discharge as the outcome, pain scores recorded by nursing and physical therapy, complications, and any 30-day post discharge emergency department ED visits. Range of motion will be recorded during the daily physical therapy sessions by PT professionals with a goniometer. Range of motion then be assessed again in clinic at the first post-operative visit. Edema- thigh circumference will be calculated at the superior pole of the patella both prior to the surgery and daily post-operatively.All these outcome scores are done routinely as standard of care and they are recorded in patients charts in EPIC.

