# **Risk/Benefit**

#### Risks

i. Skin irritation: four prior studies mention skin irritation or thermal damage with IFC use [10-13]. Two of these studies were using IFC materials from older generation products [10, 11]. In one case report by Ford et al. [13] using IFC after total knee arthroplasty, the issues was theorized to be due to placement near the infrapatellar branch of the saphenous nerve which can be frequently insensate after total knee arthroplasty.

1. In order to limit risk, leads will be placed above and below the dressing to avoid skin irritation due to insensate skin.

2. Patient determined settings will be recorded during pre-operative visit prior to anesthesia local nerve block/spinal injection to prevent patients with slightly diminished sensation post-operatively from using too high a setting.

Loss of concentration, drowsiness, decreased alertness- One case report described a patient having temporary symptoms of loss of concentration, drowsiness, decreased alertness and gait disturbances for 4-5hours after IFC treatment. The reason was theorized to be opioid like reaction due to endogenous opioid release [14]. Although a rare risk, patients will be monitored in the hospital setting by medical staff throughout their admission and use of IFC treatment.

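### The protocol names thermal skin injury as a risk, yet allows sleep during stimulation and pads left on, with no skin check or stopping rule at any session

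*Combined protocol and SAP*

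**What the plan says.** The Risks section states that "four prior studies mention skin irritation or thermal damage with IFC use". It relates one case after knee arthroplasty to electrodes near a nerve territory that often has no feeling after that operation; the reference list gives the title of that report as a full-thickness burn. Two safeguards follow. On placement, "leads will be placed above and below the dressing to avoid skin irritation due to insensate skin". On intensity, the patient's setting is recorded before the block or spinal, because sensation may be somewhat reduced afterward.

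Study Design describes the sessions. The setting is found before surgery by raising the intensity until it is slightly uncomfortable and then backing off. It is carried forward: "We will use previously established intensity values for each patient". "Once the intensity is set the program will lock automatically after 1 minute of inactivity", and the device switches itself off after 30 minutes. On what the patient may do meanwhile: "During the time when the device is working, the patient can do any regular activity such as ambulating, physical therapy or sleep without concern". Between sessions, "The electrode has an adhesive pad that can remain on the patient post-operatively if desired"; removal and replacement for each session is the stated alternative.

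Staff contact is written in. At placement, "a health care provider will place the pre-packaged sterile electrode", and under the primary outcome "patients will be asked to rate their pain based on a set VAS pain scale twice a day before the IFC treatment". The Risks section also says that medical staff will monitor patients during the admission and while the device is in use, in the paragraph on drowsiness.

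**The concern.** Both safeguards are fixed before current flows. Placement steers away from skin presumed numb, and the pre-operative setting limits the intensity. Neither shows, on the day, that the skin under a pad is tolerating the treatment.

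If that skin feels less than it did before surgery, a setting that was comfortable then may no longer give the patient a warning. A sleeping patient is less likely to report a problem, and a pad left in place hides the skin until someone lifts it. The protocol names the risk in one section, and in another gives a general reassurance with no step that would catch an early reaction. At stake is an avoidable skin injury in a patient whose ability to notice it may be reduced.

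**Working it through.** **1. Where the protocol addresses skin injury.**

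| Step | What the protocol provides | Acts when |
|---|---|---|
| Pad placement (Risks, item 1) | Above and below the dressing | Before the session |
| Intensity (Risks, item 2; Study Design) | Set before surgery, just under discomfort | Before the session |
| Pre-treatment contact (primary outcome) | VAS pain rating only | Before the session |
| During stimulation (Study Design) | 30-minute shut-off; any activity, including sleep | During |
| Staff monitoring (Risks, drowsiness paragraph) | General; names no skin check | During |
| Between sessions (Study Design) | Pads may stay on | After |
| Complications; adverse event reporting within 5 business days (Data and Safety Monitoring) | Recording and reporting | After an injury |

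No row contains a look at the pad sites or a rule to lower or stop stimulation.

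**2. Exposure.** 2 sessions per day × 2 days = 4 sessions; 4 × 30 min = 120 min per patient. At 25 per group, 25 × 4 = 100 active sessions. Sessions with a required skin check: 0 of 100. This counts the gap in the text; it does not measure risk. The document gives no injury rate.

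**3. What a rule to stop could cost in power.** This prices the remedy and is not evidence of the problem.

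- Inputs (Power/sample size): control mean 84.2 mg, SD 44.7, 30% reduction, two-sided 0.05. Assumed: the same SD in both groups.
- Planned contrast: 0.30 × 84.2 = 25.26 mg.
- The plan's own figure: n = 2 × (1.960 + 0.842)² × 44.7² / 25.26² = 49.2, so 50 per group, as stated. With the t distribution it is 50.1, and power at 50 is 79.9%.
- Assumed: a fraction f of the active dose is lost and the effect is proportional to dose, so the contrast is 25.26 × (1 − f). Power is from the noncentral t.

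| Dose lost (assumed) | Contrast, mg | Power, 25 per group | Power, 50 per group |
|---|---|---|---|
| 0% | 25.26 | 49.9% | 79.9% |
| 2% | 24.75 | 48.4% | 78.3% |
| 5% | 24.00 | 46.0% | 75.7% |
| 10% | 22.73 | 42.2% | 71.2% |

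For scale, one active patient stopped after the first session loses 3 of the 100 sessions (3%), and three such patients lose 9%. A rule that acts only on a visible skin reaction would have to stop more than three of 25 patients that early to reach the last row.

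**4. Staff time.** 50 patients × 4 sessions × 3 min (assumed) = 600 min = 10 h. At 2 to 5 min per session the range is 400 to 1,000 min, or 6.7 to 16.7 h.

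**The case against.** The best reply is that the protocol identified this risk and acted on it. Placement answers the mechanism suggested in the one arthroplasty case, and the pre-operative setting sits below discomfort and is chosen with normal sensation. The device stops itself after 30 minutes, so pads left on carry no current between sessions, and leaving them on is optional. Staff monitoring is worded broadly enough to cover all device use. Two of the four cited skin reports involved older products. Inspecting a pad site is bedside practice that may sit in a device manual or nursing procedure outside this document.

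Much of this stands, and it is why the point is low in severity. It does not close the gap. The monitoring sentence names neither skin nor a threshold for action, and no manual or procedure is cited for pad-site checks. If one exists, a one-line reference would settle most of the matter.

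A reader might infer more than the text supports:

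- *That the lock prevents a patient or nurse from turning the intensity down.* Nothing says so; it may only guard against accidental changes.
- *That sessions should be withheld or pads moved where light touch is absent, and patients kept awake.* These are debatable trade-offs. Patients are to have a block or spinal, so absent touch could cluster in the first sessions, inside the 24- and 48-hour primary window. Under the model above, losing one session in four (25%) would cut power to 31% at 25 per group. Moving pads could also shift where the two currents cross.
- *That a patient whose session is stopped becomes a dropout.* The dropout rule covers patients who leave the study or miss follow-up, and a stopped session is neither.

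**Conclusion.** The point holds as a low-severity, low-cost precaution. The protocol names thermal skin injury and expects reduced sensation, gives permissive session instructions, and requires a skin check at none of the 100 planned active sessions. Following it as written is somewhat less safe than adding a brief look at contacts that already exist.

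It would be tempting to conclude that patients are exposed to a demonstrated burn hazard, or left unobserved. The documents support neither. They do not show that skin beyond the dressing lacks feeling, they give no injury rate, and they provide for general monitoring and automatic shut-off. The number of injuries that a check would prevent cannot be estimated. The power figures rest on assumed dose losses, an assumed proportional effect and equal SDs. They show only that a rule to stop on a visible skin reaction should cost little if such reactions are uncommon.

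**What to change.** In the treatment instructions of Study Design, for both arms alike so that procedures match and the single blind is kept:

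1. Delete the reassurance that ends the sentence on activities during stimulation, and tell patients to report burning or discomfort at once.
2. At the existing pre-treatment VAS contact, and again after each session, lift the pads and inspect the skin. Stop stimulation for blistering or persistent redness.
3. Treat the recorded pre-operative setting as a ceiling, with downward adjustment only. Record the delivered intensity and the skin finding each time.

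The cost is one short paragraph, one form line per session, and about 12 minutes of existing staff time per patient (10 h over 50 patients at the assumed 3 minutes per session). Some dose is lost where a session is lowered or stopped: about 4 points of power at 25 per group if 5% of the dose goes, and about 8 points if 10% goes. Sample size, randomization and endpoints do not change.

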# b. Power/sample size

We will need a sample of 50 subjects in each group to have 80% power to detect a 30% reduction in mean 48 hour opioid use at a two-sided 0.05 significance level, assuming a mean 48 hour opioid use of 84.2mg and a standard deviation of 44.7 in the standard of care group. For this study, we anticipate to start with 25 patients per group.

Drop out/loss to follow up rate: If any patient who is assigned to treatment group decides to leave the study for any reason or any point of the study, they will be dropped out of study. Similarly, if the patient does not show up to post-operative follow up, they will be dropped from the study. The post-op follow up rates are almost at 100%, so we do not anticipate to have more than 10% drop-off. After any potential drop-offs, we aim to have 20 subjects per group at the end of this study.

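### Outcome monitoring is named only up to the first (about 2-week) clinic visit, yet the 30-day ED outcome closes around post-op day 32-33 and nothing is assigned to the 6-week visit that could capture it

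*Combined protocol and SAP*

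**What the plan says.** All of the following is in the combined protocol and SAP.

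- **When outcomes are monitored.** The outcomes part of Study Design names two occasions: the immediate post-operative period in hospital, "as well as at during the first post-op visit".
- **Visit schedule.** The same paragraph says: "Typically, patients have a follow-up visit at 2 weeks and 6 weeks after surgery". Earlier, Study Design says: "The patients will be followed until their 6 weeks post-op office visit".
- **Length of stay.** The hospital stay "varies between 48-72 hours post-operatively".
- **Post-discharge outcomes.** The secondary outcomes include "complications, and any 30-day post discharge emergency department ED visits".
- **Source.** The secondary outcomes paragraph closes with: "All these outcome scores are done routinely as standard of care and they are recorded in patients charts in EPIC".
- **Outcomes tied to a clinic visit.** Range of motion is the only one: "Range of motion then be assessed again in clinic at the first post-operative visit".
- **Attendance.** Under Power/sample size: "The post-op follow up rates are almost at 100%, so we do not anticipate to have more than 10% drop-off". The same paragraph removes from the study any patient who does not attend post-operative follow-up.
- **Re-admission.** The Objective section names a lower re-admission rate as a possible implication. Re-admission is not among the outcomes in Study Design or the variables under Data analysis.

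**The concern.** A 30-day post-discharge count can only be completed once the 30 days are over. The plan names monitoring that ends well before that, and it does not say how events in the remaining days are to be found. No question to the patient, telephone call or check of outside records is described. No later section fills the gap: the variable list under Data analysis names neither ED visits nor complications, and the Data and Safety Monitoring Board section says how fast adverse events must be reported but not how those after discharge come to light.

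At stake is the completeness of the ED-visit and complication counts. The groups are small, with 20 per group intended at the end of the study, so one event missed in an arm moves that arm's proportion by 1/20 = 5 percentage points. The drop-out rule could add to the problem: a patient who misses the clinic because of a complication treated elsewhere would be removed from the study rather than counted.

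**Working it through.** The plan states no figure for how much of the 30-day window its monitoring covers, so there is none to reproduce. Its one computed figure, the sample size for 48-hour opioid use, has no bearing on this point. What follows is calendar arithmetic.

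**Inputs**, counted in days after surgery:
- Discharge: day 2 to day 3 (stay of 48-72 hours, Study Design).
- First clinic visit: 2 weeks, taken as day 14.
- Second clinic visit: 6 weeks, taken as day 42.
- ED window: 30 days from discharge.

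**Formulas**
- Window closes = discharge day + 30.
- Window days before a visit = visit day − discharge day, with a maximum of 30.
- Window days after a visit = 30 − window days before it.

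| | Discharge day 2 | Discharge day 3 |
|---|---|---|
| Window closes | 2 + 30 = day 32 | 3 + 30 = day 33 |
| Window days before the day-14 visit | 14 − 2 = 12 (40%) | 14 − 3 = 11 (37%) |
| Window days after the day-14 visit | 30 − 12 = 18 (60%) | 30 − 11 = 19 (63%) |
| Window days after the day-42 visit | 0 | 0 |
| Days from window closing to the day-42 visit | 42 − 32 = 10 | 42 − 33 = 9 |

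**Reading the result.** Between 60% and 63% of the window falls after the last visit at which the plan says outcomes are monitored, and no scheduled contact falls in that stretch. None of the window falls after the last planned visit. A suitable visit therefore already exists, and the plan gives it no outcome to collect.

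**The case against.** The strongest reply is that follow-up does not stop at 2 weeks. Study Design follows patients to 6 weeks, and the sentence on monitoring does not say that nothing is collected later. An outcome defined over 30 days implies later collection. A count of this kind needs no contact during the window, only ascertainment after it closes, and charting continues after day 14. This stands. A reader might infer from the arithmetic that about 60% of the window goes unobserved. The documents do not support that: 60-63% is the share of the window after the first visit, not a share of data lost.

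A reader might also infer that ED visits at other hospitals will be missed. That is not shown either. The documents do not say whether EPIC displays outside encounters or whether clinic staff ask patients about them, and they give no rate of outside ED use. The EPIC sentence speaks of routinely recorded scores, so its application to ED visits is itself a reading, although no other source is given.

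The Data and Safety Monitoring Board section requires adverse events to be reported within 5 business days, with no 2-week cut-off. That is a genuine channel, but it sets reporting times and not a method of detection.

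Re-admission is mentioned in the Objective only as something that could follow from better outcomes. It is not a declared endpoint, so its absence is not a failure to measure a stated objective. It is simply cheap to collect alongside ED visits.

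Finally, these are secondary outcomes that the sample size was not built on, and Study Design says that the same outcomes are recorded in the placebo group. Nothing in the documents points to different capture in the two arms. This limits the weight of the point but does not remove it.

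**Conclusion.** The point holds as a gap in ascertainment. The plan names outcome monitoring only in hospital and at the first post-operative visit, gives routine charting as its only source, and leaves the 6-week visit without an outcome, although that visit falls 9-10 days after the ED window closes. ED visits and complications after the first visit may be under-counted, most plausibly those treated elsewhere. The size of any loss cannot be computed from the documents.

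The primary outcome, opioid use over 24 and 48 hours, is collected in hospital and is unaffected. The change is worth making because it is cheap and improves the post-discharge counts, not because the trial's main result is at risk.

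The figures assume that the first post-operative visit is the 2-week visit on day 14, that the 6-week visit is on day 42, and that discharge falls on day 2-3. The plan calls the visit times typical and the length of stay an average, so individual patients will differ.

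**What to change.** 1. **Study Design, outcomes.** Make the 6-week visit the closing assessment in both arms. Ask every patient, in the same words, about any ED visit, re-admission or complication since discharge, at any hospital, with dates. Combine the answers with the chart record.
2. **Counting rules.** Count ED visits to 30 days after discharge, using the dates to exclude later ones. Count complications and re-admissions to 6 weeks.
3. **Power/sample size, drop-out paragraph.** Amend it so that patients who miss a follow-up visit are not dropped and keep their chart-derived events. Without this change, the new text in Study Design would contradict the existing rule.

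The cost is three questions and three form fields at a visit that is already planned and that the plan expects nearly all patients to attend. The downside is minor recall error in self-reported dates, which matters mainly for events near day 30 after discharge and can be checked against the chart where a record exists.

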# 4. Data analysis

We hypothesize that IFC therapy will improve patient's pain management and range of motion as well as decrease soft tissue edema after TKA when compared to control group. Study variables: total opioid consumption per 24h and 48h, VAS pain scale, KOOS pain score, range of motion, thigh circumference, 6-click AMP scores.

The significance level of the test was targeted at 0.05.

All outcomes and PT exam measures will be summarized as mean, standard deviation, and range. Differences between means will be analyzed with a Student's t-test or Mann-Whitney U test.

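### The primary opioid outcome is set at both 24 h and 48 h, with no rule for which decides success; the sample size covers 48 h only

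*Combined protocol and SAP*

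**What the plan says.** Three parts of the combined protocol and SAP bear on this.

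- **Study Design, item 1 (primary outcome).** The primary outcome "will be the post-operative pain medication usage during the first 24 and 48 hours". The two windows are named together and not ranked. The same section says that opioid use is taken from nurse-reported records of doses given, and that the average hospital stay "varies between 48-72 hours post-operatively".
- **Study Population, b. Power/sample size.** "We will need a sample of 50 subjects in each group to have 80% power" for a 30% "reduction in mean 48 hour opioid use at a two-sided 0.05 significance level". The control mean is 84.2 mg and the SD 44.7, both for 48 hours. No 24-hour mean, SD or effect is given. The section continues: "For this study, we anticipate to start with 25 patients per group", and after drop-out "we aim to have 20 subjects per group at the end of this study".
- **Data and Safety Monitoring, 4. Data analysis.** "Study variables: total opioid consumption per 24h and 48h", followed by the other measures in the same list. The only statement on error control is "The significance level of the test was targeted at 0.05". All outcomes are to be compared by t-test or Mann-Whitney test.

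No section ranks the two time points, says whether one or both must be significant, or adjusts for testing two.

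**The concern.** A primary outcome measured at two times gives two tests, and the plan needs a rule for turning two p-values into one conclusion. Without one, three readings are open: 48 h decides, either suffices, or both are required. They differ in false-positive rate and in the chance of success. If the results disagree, the reading would be chosen after the data are seen.

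The sample-size section, and the reference to a single test in Data analysis, suggest that 48 h was meant. But the basis of a sample-size calculation is not a decision rule, and the section that defines the primary outcome does not separate the two windows.

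**Working it through.** **1. Reproduce the plan's sample size.** Inputs from Power/sample size: control mean 84.2 mg, SD 44.7 (taken as common to both groups), 30% reduction, two-sided 0.05, 80% power. Allocation is 1:1 (Randomization).

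- Difference = 0.30 × 84.2 = 25.26 mg; standardised effect d = 25.26 / 44.7 = 0.565.
- n per group = 2 × (1.960 + 0.842)² / 0.565² ≈ 49.2, rounded up to 50. The noncentral t calculation gives 50.1.

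The stated 50 per group is therefore correct, for 48 h only.

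**2. Power for 48 h at the planned sizes** (noncentral t, d = 0.565, alpha 0.05): 79.9% at 50 per group, 49.9% at 25 and 41.4% at 20.

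**3. Correlation between the two totals.** The documents give none, so a range is assumed. The 0–24 h total is part of the 0–48 h total. With equal variances on the two days and between-day correlation ρ, the correlation of the totals is r = √((1 + ρ)/2).

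- ρ = 0 gives r = 0.71, and ρ = 0.5 gives r = 0.87.
- r = 0.95 corresponds to ρ = 2 × 0.95² − 1 = 0.805.
- r = 0.5 needs ρ = −0.5 or, with uncorrelated days, a day-2 variance three times that of day 1, since 1/√(1 + 3) = 0.5.

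**4. Error rates and split results.** Under no effect, P(at least one significant) = 1 − P(|Z₁| ≤ 1.96 and |Z₂| ≤ 1.96) for a bivariate normal with correlation r, and P(both) = 0.10 − P(at least one). The last two columns are from 100,000 simulated trials per setting with d = 0.565 at both times. For 24 h that effect is an assumption.

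| r | False positive, either suffices | False positive, both required | Exactly one significant, 25 per group | Exactly one significant, 20 per group |
|---|---|---|---|---|
| 0.5 | 9.1% | 0.9% | 34% | 33% |
| 0.71 | 8.3% | 1.7% | 26% | 25% |
| 0.87 | 7.3% | 2.7% | 17% | 17% |
| 0.95 | 6.5% | 3.5% | 10% | 10% |

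The limit for independent tests is 1 − 0.95² = 9.75%. Simulated t-tests (200,000 trials) at 25 and 20 per group agree with the either-suffices column to within 0.1 percentage point. The both-required column assumes no effect at either time; with a true effect at one time only, that rule's false-positive rate is still at most 5%.

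**5. Chance of success under each reading, 25 per group, d = 0.565 at both times.** The two powers sum to 2 × 0.499 = 0.998, and P(either) − P(both) is the split rate.

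- r = 0.5: either = (0.998 + 0.336)/2 = 67%; both = (0.998 − 0.336)/2 = 33%.
- r = 0.95: either = (0.998 + 0.103)/2 = 55%; both = (0.998 − 0.103)/2 = 45%.
- 48 h alone: 50% whatever the correlation.

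**6. Cost of splitting alpha instead.** At 0.025 per time point, 48 h power is 70.8% at 50 per group, 38.4% at 25 and 30.4% at 20. Restoring 80% would take 61 per group.

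**The case against.** The strongest reply is that 48 h is already implied. It is the only quantified hypothesis, the significance statement speaks of one test, and the two nested windows can be read as one outcome reported cumulatively. On that reading there is no inflation, nor is there any if both time points are required. This narrows the point to a missing rule rather than a demonstrated error rate above 5%. But the implication has to be inferred, and the section that defines the primary outcome does not support it over the alternatives.

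The low correlations can also be challenged. Values below 0.71 need negatively correlated days or a much more variable second day, and positive correlation is more plausible. The more credible range is then 0.71 to 0.95, where the either-suffices error is 6.5% to 8.3% and splits at 25 per group occur in 10% to 26% of trials. That is smaller, but the error is still above 5%. The split rates also rest on an assumed 24 h effect.

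Two wording points stand without changing the remedy. The primary-outcome paragraph speaks of pain medication, while the sample size and analysis use opioids. It also mentions a twice-daily VAS rating without giving its status. Finally, the shortfall from 50 to 25 or 20 per group is a separate problem; here it only explains why split results are likely.

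**Conclusion.** The concern holds and should be fixed. The primary outcome is unranked at two time points, the analysis has no decision rule, and the sample size covers one of them. If either time point may be claimed, the false-positive rate is 6.5% to 9.1% for correlations of 0.95 to 0.5 (6.5% to 8.3% for 0.95 to 0.71) against the stated 5%. If both are required, it does not exceed 5%. At 25 per group the plan would be unable to call the result in 10% to 34% of trials, if the planned standardised effect held at both times.

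That the rule is missing can be read directly from the text. The percentages are illustrations: the documents give no success rule, no correlation and no 24 h effect, and the calculations use normal-theory tests.

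**What to change.** First have the sponsor confirm that pain medication in the primary outcome means opioids, as in the sample-size and Data analysis sections. Then, in Study Design item 1 and in Data analysis, adopt one of these:

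- total opioid consumption from 0 to 48 h is the single primary endpoint, tested two-sided at 0.05, with 24-hour opioid use secondary; or
- both stay primary in fixed order: 48 h at 0.05, then 24 h at 0.05 only if 48 h is significant.

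Either holds the primary claim at 5%, matches the existing sample-size calculation and costs the 48 h test no power. An equal alpha split is worse: 48 h power would fall from 50% to 38% at 25 per group and from 41% to 30% at 20.

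The cost is one or two sentences in each section, with no new patients or measurements. There are three drawbacks:

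- A significant 24-hour result alone could no longer be claimed as primary success.
- Because the total comes from in-hospital records, anyone discharged before 48 h would have an incomplete total. This already affects the 48 h outcome but matters more once 48 h decides alone, so the plan should state how such patients are counted.
- The change does nothing for the low power at 25 or 20 per group.
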